7.2 Methods and Timing for Assessing, Recording, and Analyzing Safety Parameters

Safety monitoring will occur continuously throughout the study using both active and passive monitoring methods outlined and discussed in further detail below. All reported AEs, SAEs, and unanticipated problems will be recorded throughout the study using the data collection systems set up and detailed in the Data and Safety Monitoring Plan (DSMP)

The research staff will record all reportable events with start dates occurring any time after informed consent is obtained but no later than the final 1-year assessment. At each study visit, the research staff will inquire about the occurrence of AE/SAEs since the last visit (or time of most recent reporting). Events will be followed for outcome information until resolution or stabilization or until the grant funding ends.

7.3 Adverse Events and Serious Adverse Events, Reporting Procedures, and Follow-up

An adverse event (AE) is generally defined as any unfavorable and unintended diagnosis, symptom, sign (including an abnormal laboratory finding), syndrome or disease which either occurs during the study, having been absent at baseline, or if present at baseline, appears to worsen. A serious adverse event (SAE) is generally defined as any untoward medical occurrence that results in death, is life threatening, requires inpatient hospitalization or prolongation of existing hospitalization, results in persistent or significant disability/incapacity, or is a congenital anomaly.

Per NCCIH safety monitoring requirements, all AEs and SAEs captured and/or observed involving enrolled study participants will be recorded regardless of their relationship to the study intervention. Below we outline possible AEs and SAEs that may occur related to this research study and intervention; present our procedures for capturing and recoding; and detail the protocol for follow up of AEs. For further discussion of the procedures related to safety monitoring and follow up procedures refer to Section 7.4. Safety Monitoring.

Safety Check-ins: All participants enrolled in the study, regardless of treatment allocation, will receive a two-tiered safety monitoring 'check-in' every 2 weeks during the treatment phase of the study; every month during months 3-6 of the follow-up phase; and at the final 1-year time point. The two-tiered system is designed to detect and follow up on AEs that are at least moderate in severity (interfere with ADL), and to minimize staff and participant burden that would otherwise occur if all mild events were queried and documented.

Tier 1 of the safety check-in involves sending all active, enrolled participants an email (or placing a phone call from a research staff member, if no email provided) containing a link to a brief online survey that queries events with moderate or greater levels of severity. Any participant who endorses one or more tier 1 questions will automatically receive a tier 2 survey and follow-up phone call from study staff.

The Tier 2 survey specifically queries the most common meditation-related side effects (e.g. anxiety, depression, dissociation, flashbacks etc.) using patient-reported outcomes measurement information system (PROMIS) or NeuroQol items (or other validated scales if construct is not available), and PROMIS response options (never- very often).

Additionally, the tier 2 survey will ask participants to provide further detail (i.e., date of onset, symptomology, circumstance surrounding the event, relatedness to the intervention, etc.) regarding the AE/SAE reported in the tier 1 survey. Detail provided will be used to guide the tier 2 phone calls made by research study staff.

Tier 2 Safety Check-in phone call: Any participant who indicates that he or she experienced an AE or SAE will then receive a follow up call from a trained research staff member. The purpose of the follow up call will be to further document the details of the AE/SAE, assess need for treatment modification, referrals and reporting.

Research staff members conducting the safety monitoring phone interviews will document the details of the AE/SAE using the Adverse Events Form, which will then be included in the participant file as well as in the annual Data Safety Monitoring Reports presented to the DSMB. Reporting procedures for AEs and SAEs related to the study will be followed including reporting all SAEs to the study PI and DSMB committee chair.

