All study staff will be blinded to the participant treatment allocation with the exception of the instructor, individual who performs the randomization, and staff member coordinating participants within each course. All staff performing participant assessments will be blinded to the participant treatment allocation to promote equipoise. Data analyses will be performed by a statistician blinded to treatment allocation type. The data manager will be able to break blinding if needed (e.g. for Data and Safety Monitoring Board).

Intervention Allocation

Stratified randomization will be used, as simple randomization can fail if it creates groups unbalanced for critical features known to affect outcomes.^{7,8} Stratified randomization can reduce both types I and II error, improve trial efficiency, and facilitate subgroup and interim analyses.⁷ Randomization will be done using an online computer software program known as Research Randomizer (Version 4.0).⁹ The randomization process will occur after each new round of enrollment. Study enrollment will continue until target enrollment goals are reached (i.e., n=50 for MBBP intervention group, n=50 for enhanced usual care control group).

Interventions and Duration

Two-arm RCT comparing MB-BP vs. enhanced usual care. Follow-up assessments will take place within pre-defined assessment windows occurring around 10 weeks, 6 months, and 1 year post- intervention commencement. For participants on waitlist enhanced usual care, they will be offered MB-BP after the 6-month follow-up with no additional assessments unless they would like the assessments for follow-up information on changes in their health. Participants in the intervention group will be asked to come back at the 1-year follow up window for an abbreviated follow up assessment. Thus the total length of involvement for study participants will be up to one year from the time of enrollment to the time of the final research assessment. The study intervention lasts 9 weeks, may be nonconsecutive weeks in the event of a holiday or instructor availability, and takes place in the first three months for individuals in the intervention arm.

Sample Size and Population

We anticipate needing to recruit and enroll a total of 100 eligible individuals during Phase 3. This will consist of 50 individuals per group for both the MB-BP intervention arm and the enhanced usual care arm. (see Figure 1 below for detail).

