Baseline assessments for all enrolled participants will take place within four weeks of the start of the intervention. Follow-up assessments will take place during the 10 week, 6 month, and 1 year assessment windows, which are defined as: (a) “10 week” follow up assessments are to occur at least one day after and up to five weeks after the end of the intervention (i.e. the Week 8 class). Staff will prioritize completing the assessments within the first three weeks of the assessment window, but will allow for participants to complete up to five weeks after. (b) The “6-month” follow up assessments will be scheduled to occur six months from the orientation class date plus or minus 2.5 weeks. This allows for a five-week data collection period with prioritization given to the three-week window surrounding the official six-month date. (c) The “1 year” follow up assessments are to be completed with the intervention group participants only and will occur one year plus or minus a month after the start of the intervention (i.e., orientation date).

If a participant is unable to complete an assessment within the defined data collection window, but still wishes to participate, we will allow for the participant to complete an online home survey and/or in person follow up assessment beyond the parameters defined above.

Participants who were randomized to the waitlist enhanced usual care group will be offered MB-BP after the 6 month follow-up assessment is complete with no additional assessments unless they would like the final one year assessment for follow-up information on changes in their health. Thus the total length of involvement for study participants will be up to one year from the time of enrollment to the time of the final research assessment. The study intervention lasts 9 weeks and takes place in the first two months for individuals in the intervention arm. The intervention will be offered several times a year over the course of the total study duration.

Prehypertension/Hypertension Medical Regimen Adherence Outcomes Assessment Methods:

Primary Prehypertension/Hypertension Medical Regimen Adherence Outcome: Dietary Approaches to Stop Hypertension (DASH) eating pattern score,¹⁸¹ measured via 80-item Willet food frequency questionnaire,¹⁸² assessing adherence to American Heart Association/American College of Cardiology (AHA/ACC) clinical practice hypertension guidelines DASH eating pattern score (range 0-8).^{10,181,183}

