Study enrollment will continue until target enrollment goals are reached (i.e., n=50 for MBBP intervention group and n=50 for enhanced usual care control group).

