6.2.7 Completion/Final Evaluation

For control group participants, the 6-month evaluation is the final visit. Upon completion of this assessment, they will be eligible to participate in the MB-BP training. Individuals in the intervention group will be assessed at 1 year follow up with a subset of measures (see Table 6.1 Schedule of Evaluation) in order to assess long term effects of the intervention.

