7.3.1 Mental Health

Participants assigned to any treatment group may experience mental health or suicidal ideation during the course of their study involvement. All study participants will be monitored for AEs and SAEs by study staff on a monthly basis until the time of their study completion. Additionally, participants will be asked to complete questionnaires about anxiety, depression and suicidal ideation, specifically the Beck Anxiety Inventory and the Center for Epidemiology Study Depression Scale Revised (CESD-R), at each of their in-person assessments, excluding the one year follow up. [name], a licensed psychiatrist with extensive experience evaluating research participants for clinical deterioration or suicidality, will serve as the study clinician.

Beck Anxiety Inventory (BA): If participant scores ≥ 26 on the Beck Anxiety Inventory, a safety flag will appear notifying the research assistant (RA) administering the assessment. The RA will then implement the MB-BP safety protocol, which is reviewed and approved by the Brown University IRB. Staff are trained on the safety protocol and a hard copy of the protocol is kept in an accessible location in the assessment office at all times.

Depressive Symptomatology: The CESD-R will be administered during the in-person assessment visits, and scores will be reviewed immediately upon completion of the in-person assessments.

1. Sadness (dysphoria): Question numbers 2,4, 6
2. Loss of Interest (anhedonia): Question numbers 8, 10
3. Appetite: Question numbers 1, 18
4. Sleep: Question numbers 5, 11, 19
5. Thinking / concentration: Question numbers 3, 20
6. Guilt (worthlessness): Question numbers 9, 17
7. Tired (fatigue): Question numbers 7, 16
8. Movement (agitation): Question numbers 12, 13
9. Suicidal ideation: Question numbers 14, 15

Participants are considered to meet criteria for major depressive episode if they have anhedonia or dysphoria nearly every day for the past two weeks, plus symptoms in an additional 4 DSM symptom groups noted as occurring nearly every day for the past two weeks. If participants meet criteria for major depressive episode, a safety flag will appear notifying the research

assistant (RA) administering the assessment. The RA will then implement the MB-BP safety protocol, which is reviewed and approved by the Brown University IRB. Staff are trained on the safety protocol and a hard copy of the protocol is kept in an accessible location in the assessment office at all times.

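### Section 7.3 schedules no safety check-in between month 6 and 1 year, the period in which waitlist controls are offered MB-BP, and Section 7.3.1 promises something different for those months

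*Combined protocol and SAP*

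**What the plan says.** Section 7.3 (Safety Check-ins) sets one schedule for all enrolled participants whatever their allocation: two-weekly in the treatment phase, "every month during months 3-6 of the follow-up phase; and at the final 1-year time point". The check-in is an emailed survey, or a phone call where there is no email. A positive answer leads to a second survey and a staff call.

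Section 3 says that waitlist participants "will be offered MB-BP after the 6 month follow-up assessment is complete with no additional assessments unless they would like" a one-year assessment. It reserves the scheduled one for the other arm: the 1-year "follow up assessments are to be completed with the intervention group participants only". Section 6.2.7 adds: "For control group participants, the 6-month evaluation is the final visit". The Protocol Summary and Section 3 nevertheless describe involvement of up to one year for study participants in general.

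Section 7.3.1 says that all participants will be "monitored for AEs and SAEs by study staff on a monthly basis until the time of their study completion". Section 7.2 records events from consent until no later than the final 1-year assessment, and has staff ask about events at each study visit. Section 7.1 has teachers ask class participants about their experience of meditation. It explains that the online check-in exists because some people are not comfortable raising difficulties in class. Section 7.3.3 allows self-report at any time.

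**The concern.** The check-in schedule follows the calendar of the study, not the start of exposure. Controls are surveyed most often while they receive no meditation training. If they later take the course, the structured survey designed to detect its side effects is not scheduled, and no text restarts it.

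Two things are at stake. One is timely detection of the meditation-related effects listed in Section 7.1 among people who are doing the course. The other is information: Section 7.1 puts serious effects at an estimated rate below 1% but concedes that adequate estimates are lacking, and waitlist courses could add materially to the number exposed. Separately, staff cannot tell from Sections 7.3 and 7.3.1 what contact anyone in either arm should receive in months 6-12. The randomised comparison of MAIA is not affected.

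**Working it through.** **Inputs.** Section 6.2.4 gives "n=50 for MBBP intervention group and n=50 for enhanced usual care control group". The course lasts 9 weeks (Protocol Summary, Section 3). Dropout averages 10-15% per group and is highest in controls (Section 9.2). Uptake of the waitlist offer is not stated; 25%, 50% and 100% are assumptions. All 50 in the MB-BP arm are counted as exposed.

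**Check-ins during the course (Section 7.3).**
- Randomised MB-BP arm: 9 weeks / 2 = 4.5, so about 4-5.
- Control taking the course between month 6 and 1 year: 0.

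**Months 6-12, MB-BP arm.** Their last assessment is at 1 year, so completion cannot be earlier for those who stay in the study. Section 7.3.1 then implies about 6 monthly contacts; Section 7.3 lists 1, at 1 year.

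**Months 6-12, controls.** If completion is the final visit at month 6 (Section 6.2.7), the monthly monitoring in Section 7.3.1 stops before the waitlist course. If completion is at one year, Section 7.3.1 covers a course taken within that year, but Section 7.3 has no contact to deliver it. The text does not choose.

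**Share of all exposed people who are waitlist controls.** With c = 50 x (1 - dropout) x uptake, the share is c / (50 + c).

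| Uptake | No dropout | 10% dropout | 15% dropout |
|---|---|---|---|
| 100% | 50/100 = 50% | 45/95 = 47.4% | 42.5/92.5 = 45.9% |
| 50% | 25/75 = 33.3% | 22.5/72.5 = 31.0% | 21.25/71.25 = 29.8% |
| 25% | 12.5/62.5 = 20% | 11.25/61.25 = 18.4% | 10.625/60.625 = 17.5% |

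**What no observed event can rule out.** The one-sided 95% upper bound with zero events in n people is 1 - 0.05^(1/n).
- n = 50 (randomised arm only): 5.8%.
- n = 92 to 95 (full uptake after 15% to 10% dropout): 3.2% to 3.1%.
- n = about 72 (50% uptake): 4.1%.
- n = about 61 (25% uptake): 4.8%.

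The gap between 5.8% and the other figures is the loss only if no waitlist-course event is captured at all.

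**The case against.** A reader might infer that up to half of everyone exposed has no active adverse-event monitoring during the course, that only passive self-report remains, and that nearly half of the safety data is lost. The documents do not support that.

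- On the one-year reading of completion, Section 7.3.1 has staff monitoring controls monthly during a waitlist course taken within that year.
- Teacher querying in Section 7.1 is not limited to the randomised arm. It is weaker than the survey, for the reason Section 7.1 itself gives, but it is active enquiry.
- The 1-year check-in is worded for all participants, and the second-tier survey asks for onset date and relatedness. Events could be captured late, so delay and recall may be the problem rather than loss.
- A last visit at month 6 does not clearly conflict with a 1-year check-in, because the check-in is a survey or call and not a visit.
- Half is a ceiling that needs full uptake and no control dropout.
- Section 7.1 describes mania, psychosis and suicidality as a few case reports, mostly from intensive retreats or with pre-existing psychopathology.
- The separate Data and Safety Monitoring Plan is not among the documents and may say more.

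All of this stands, and it narrows the point without removing it. The late safeguards are uncertain. First-tier surveys go to active, enrolled participants, and whether a control still counts as one after the final visit is not stated. Section 7.3.1 omits the anxiety and depression questionnaires at one year, so even a control who opts into that assessment is not scheduled for them. Courses run only several times a year, so a waitlist course could extend beyond the recording window in Section 7.2. A separate plan could add detail, but it would not remove the disagreement between Sections 7.3 and 7.3.1.

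**Conclusion.** The point holds in this form: Section 7.3 places no check-in between month 6 and 1 year, so a control taking MB-BP in that period has 0 scheduled check-ins against about 4-5 in the randomised arm. Sections 7.3 and 7.3.1 contradict each other for the MB-BP arm in months 6-12, about 6 contacts against 1. For controls, the meaning of study completion is open, so whether staff monitoring covers the waitlist course cannot be determined.

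The people affected could be 46-50% of those exposed at full uptake, about 30-33% at 50% and 18-20% at 25%. The upper bound of 5.8%, against about 3.1-4.8% after the stated dropout, applies only if none of their events are captured. These sizes rest on assumed uptake, on the protocol's average dropout applied to controls, and on all 50 MB-BP participants being exposed. The documents do not show that monitoring is absent. They show that the structured check-in is not scheduled and that the remaining text does not settle what replaces it.

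**What to change.** - Reconcile Sections 3, 6.2.7, 7.2, 7.3 and 7.3.1 on what contact each arm receives in months 6-12.
- Define study completion for controls, including whether a control who takes the waitlist course is still an active participant and receives the 1-year check-in.
- Extend the existing two-tier check-in and adverse-event recording to cover any MB-BP course a control takes, through to the end of that course. The frequency is for the sponsor to settle when reconciling the sections.
- Tabulate waitlist-course events separately from the randomised comparison, since they are uncontrolled and arise after the 6-month assessment.

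The cost is mainly protocol wording. The survey already exists and is sent by email, so the added burden is a few automated surveys per crossover participant and follow-up calls for those who report an event.

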7.3.1 Mental Health

Participants assigned to any treatment group may experience mental health or suicidal ideation during the course of their study involvement. All study participants will be monitored for AEs and SAEs by study staff on a monthly basis until the time of their study completion. Additionally, participants will be asked to complete questionnaires about anxiety, depression and suicidal ideation, specifically the Beck Anxiety Inventory and the Center for Epidemiology Study Depression Scale Revised (CESD-R), at each of their in-person assessments, excluding the one year follow up. [name], a licensed psychiatrist with extensive experience evaluating research participants for clinical deterioration or suicidality, will serve as the study clinician.

Beck Anxiety Inventory (BA): If participant scores ≥ 26 on the Beck Anxiety Inventory, a safety flag will appear notifying the research assistant (RA) administering the assessment. The RA will then implement the MB-BP safety protocol, which is reviewed and approved by the Brown University IRB. Staff are trained on the safety protocol and a hard copy of the protocol is kept in an accessible location in the assessment office at all times.

Depressive Symptomatology: The CESD-R will be administered during the in-person assessment visits, and scores will be reviewed immediately upon completion of the in-person assessments.

1. Sadness (dysphoria): Question numbers 2,4, 6
2. Loss of Interest (anhedonia): Question numbers 8, 10
3. Appetite: Question numbers 1, 18
4. Sleep: Question numbers 5, 11, 19
5. Thinking / concentration: Question numbers 3, 20
6. Guilt (worthlessness): Question numbers 9, 17
7. Tired (fatigue): Question numbers 7, 16
8. Movement (agitation): Question numbers 12, 13
9. Suicidal ideation: Question numbers 14, 15

Participants are considered to meet criteria for major depressive episode if they have anhedonia or dysphoria nearly every day for the past two weeks, plus symptoms in an additional 4 DSM symptom groups noted as occurring nearly every day for the past two weeks. If participants meet criteria for major depressive episode, a safety flag will appear notifying the research

assistant (RA) administering the assessment. The RA will then implement the MB-BP safety protocol, which is reviewed and approved by the Brown University IRB. Staff are trained on the safety protocol and a hard copy of the protocol is kept in an accessible location in the assessment office at all times.

If participants respond having any suicidal ideation (CES-D questions 14 or 15), staff will again be instructed to follow the IRB approved safety protocol.

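### Section 7.3.1 promises monthly adverse-event monitoring to study completion, but for MB-BP participants Section 7.3 schedules no check-in between the month 3–6 contacts and 1 year

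*Combined protocol and SAP*

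**What the plan says.** Section 7.3.1 makes a general commitment: "All study participants will be monitored for AEs and SAEs by study staff on a monthly basis until the time of their study completion".

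Completion differs by arm. Under Section 6.2.7 the 6-month evaluation is the last visit for controls. Section 3 says the 1-year assessments "are to be completed with the intervention group participants only and will occur one year plus or minus a month" from the orientation date. Controls "will be offered MB-BP after the 6 month follow-up assessment is complete".

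Section 7.3 gives the check-in schedule, which applies to both arms: fortnightly while treatment runs, then "every month during months 3-6 of the follow-up phase; and at the final 1-year time point". A check-in starts with a short Tier 1 survey. "Any participant who endorses one or more tier 1 questions will automatically receive a tier 2 survey" and a staff call.

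Other routes of capture are these:
- Section 7.2: at each study visit "the research staff will inquire about the occurrence of AE/SAEs since the last visit", and known events are followed until they resolve or stabilise.
- Sections 7.3.3 and 7.4: participants can report events at any time.
- Section 6.2.6: monitoring runs throughout involvement, with no frequency given.

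The depression scale (CESD-R) and the Beck Anxiety Inventory are given "at each of their in-person assessments, excluding the one year follow up", which agrees with the table in Section 6.1. Sections 6.2.6, 7.2 and 7.4 also refer to a separate safety monitoring protocol or plan (the DSMP).

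**The concern.** For MB-BP participants the two sections cannot both be followed. Staff who work to Section 7.3 make no scheduled contact for several months in which Section 7.3.1 says monitoring is monthly. Staff who work to Section 7.3.1 have no scheduled check-in to use.

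What is at stake is prompt detection of new harm in the treated arm after the month 3–6 check-ins end. Section 7.1 justifies the online check-in on the ground that some participants will not raise difficulties in class, so by the protocol's own reasoning volunteered reports are an incomplete substitute. Section 7.3.2 also relies on the routine check-ins to pick up physical injuries. Home practice is measured up to 1 year (Section 6.1), so the plan allows for practice continuing through the gap.

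The month count is also unclear. Section 7.3 attaches months 3–6 to the follow-up phase, which could mean study months or months since the course ended.

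**Working it through.** The plan states no figure for this, so the check is a calendar count.

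**Inputs**
- Promise: monthly until completion (Section 7.3.1).
- Schedule: monthly in months 3–6, then once at 1 year (Section 7.3).
- 1-year visit: month 12, plus or minus 1 month, from orientation (Section 3), so V = 11, 12 or 13.
- Course length: 9 weeks (Section 3). The protocol summary allows it to fall anywhere in the first three months.
- MB-BP arm: 50 participants.

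**Last monthly check-in, L**
- Months counted from orientation: L = 6.
- Months counted from the end of a 9-week course: 63 days / 30.44 = 2.07 months, and 2.07 + 6 = 8.07, so L is about 8.
- Months counted from the end of a course that fills three months: L = 3 + 6 = 9.

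**Unscheduled monthly contacts per MB-BP participant = V − L − 1**

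| Month count | L | V = 11 | V = 12 (nominal) | V = 13 |
|---|---|---|---|---|
| From orientation | 6 | 4 | 5 (months 7–11) | 6 |
| From end of 9-week course | 8 | 2 | 3 (months 9–11) | 4 |
| From end of three-month course | 9 | 1 | 2 (months 10–11) | 3 |

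**For 50 participants**
- From orientation: 5 × 50 = 250 nominal, range 4 × 50 = 200 to 6 × 50 = 300.
- From end of 9-week course: 3 × 50 = 150 nominal, range 2 × 50 = 100 to 4 × 50 = 200.
- From end of three-month course: 2 × 50 = 100 nominal, range 1 × 50 = 50 to 3 × 50 = 150.

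These are ceilings for full retention. No drop-out is deducted, because the 10–15% in Section 9.2 is an average across arms with controls expected to be highest.

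**Delay to the next inquiry.** Assume onset is uniform over the gap and the participant does not report the event. The mean wait is (V − L)/2.
- From orientation: (12 − 6)/2 = 3 months, range 5/2 = 2.5 to 7/2 = 3.5.
- From end of 9-week course: (12 − 8)/2 = 2 months, range 3/2 = 1.5 to 5/2 = 2.5.
- Monthly contact: 1/2 = 0.5 month.

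**Early side.** If months run from the end of the 9-week course, follow-up months 1–2 (about study months 3–4) also have no check-in, in either arm, although the 10-week visit falls near month 3.

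**Does another section fill the gap?** Section 7.2 asks at visits, and none is planned between 6 months and 1 year. Sections 7.3.3 and 7.4 wait for the participant to make contact. The continuous review in Section 7.4 covers events already documented by staff and points back to Section 7.3. Section 6.2.6 sets no frequency. None supplies a monthly contact.

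**The case against.** The strongest reply is that Section 7.3 is the specific schedule and Section 7.3.1 only a loose summary. Monthly does not match the fortnightly treatment phase either, and the sentence speaks of monitoring, not of contacting. On that view, pointing Section 7.3.1 to Section 7.3 removes the contradiction at no operational cost. That edit would make the text consistent, and reading monitoring as contact is an inference. But it would do so by withdrawing a stated safety commitment, and staff cannot monitor for new events that nobody has asked about or reported. Section 7.3 does mention limiting burden, but as the reason for not querying mild events, not for spacing out check-ins.

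Other mitigations stand. Events already open at month 6 stay under follow-up (Section 7.2), self-report is encouraged, and the 1-year visit asks retrospectively. The DSMP may hold a fuller schedule, though that would not cure the conflict within the protocol.

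Four stronger readings are tempting, and the documents do not support them:
- *The missing 1-year CESD-R and Beck screens are an error.* Sections 6.1 and 7.3.1 agree on leaving them out, so this is a deliberate choice. It is context for the gap and no part of the contradiction.
- *The comparison of harms between arms is biased.* Both arms share one schedule to month 6 on either count.
- *The 1-year check-in for controls is a mistake.* Controls may take MB-BP after month 6, so a later check-in makes sense.
- *Controls are also owed monthly contact to 1 year.* Section 6.2.7 makes month 6 their final visit, so the Section 7.3.1 promise ends there. Whether controls who then take the course should be followed more closely is a fair but separate design question.

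**Conclusion.** The inconsistency is real and confined to MB-BP participants after the month 3–6 check-ins. Nominally 5 monthly contacts per participant are unscheduled if months run from orientation (4 to 6 with the visit window), or about 3 if they run from the end of the 9-week course (2 to 4), one fewer if the course fills three months. No reading of the written schedule brings the count to zero.

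The consequence is later detection of new-onset events that are not self-reported. It does not touch the 6-month between-arm harm comparison, the sample size or the primary analysis. Few serious events are likely: Section 7.1 puts serious effects of such programmes below 1%, which is below 0.01 × 50 = 0.5 of a participant, while warning that adequate estimates do not exist. The conclusion rests on the protocol text alone, because the DSMP was not available. The point is worth correcting because the remedy is cheap.

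**What to change.** 1. In Section 7.3.1, replace the monthly sentence with a reference to the check-in schedule in Section 7.3, so that one schedule governs.
2. In Section 7.3, state that months 3–6 are study months counted from the orientation date.
3. In Section 7.3, add: *MB-BP participants also receive the Tier 1 check-in, with the usual Tier 2 escalation, each month from month 7 until their 1-year assessment.* Tying the end to the assessment, not to month 11, covers month 12 when the visit is late and avoids duplication when it is early. Keep the 1-year check-in for both arms.
4. If the count was meant to run from the end of the course, also keep the controls' check-ins in study months 7–8, so that they lose none.
5. If the DSMP already sets these contacts, state that schedule in Section 7.3 instead.

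Cost: 4 to 6 added contacts × 50 = 200 to 300 Tier 1 emails or calls if months already run from orientation. If they were meant to run from the end of the 9-week course, MB-BP gains months 3–4 plus 2 to 4 late contacts (4 to 6 × 50 = 200 to 300) and controls gain months 3–4 (2 × 50 = 100), or 300 to 400 in all. Add any resulting Tier 2 surveys, calls and forms, and the written IRB and NCCIH approval that Section 7.4 requires for amendments. The survey and escalation route already exist.
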